3.3.8.2 Concomitant Medications and Therapies

At each study visit, study site staff must question the participant regarding any medications taken and vaccinations received by the participant and record the following information in the eCRF:

- All non-study vaccinations administered within the period starting 28 days before the first study injection.
- All concomitant medications and non-study vaccinations taken through 28 days after each injection. Antipyretics and analgesics taken prophylactically (ie, taken in the absence of any symptoms in anticipation of an injection reaction) will be recorded as such.
- Any concomitant medications relevant to or for the treatment of an SAE or a MAAE.
- Participant will be asked in the eDiary if they have taken any antipyretic or analgesic to treat or prevent fever or pain within 7 days after each study injection, including the day of injection. Reported antipyretic or analgesic medications should be recorded in the source document by the site staff during the post-injection study visits or via other participant interactions (eg, telephone calls).

The use of the following concomitant medications and/or vaccines will not require withdrawal of the participant from the study but may determine a participant's eligibility to receive a second dose or evaluability in the per-protocol analysis (analysis sets are described in [Section 4.4](#)):

- Any investigational or nonregistered product (drug or vaccine) other than the study vaccine used during the study period.
- Immunosuppressants or other immune-modifying drugs administered chronically (ie, more than 14 days in total) during the study period. For corticosteroids, this will mean that prednisone \geq 20 mg/day or the equivalent is not permitted. Inhaled, nasal, and topical steroids are allowed.
- Long-acting immune-modifying drugs administered at any time during the study period (eg, infliximab).
- A licensed vaccine administered during the period from 28 days before through 28 days after each study injection, except for any licensed influenza vaccine that was administered more than 14 days before or after any study injection.
- Immunoglobulins and/or any blood products administered during the study period.

Concomitant medications (including vaccinations) will be coded using the WHO Drug Dictionary. If a participant takes a prohibited drug therapy, the investigator and the CRO's medical monitor will make a joint decision about continuing or withholding further injection of the participant based on the time the medication was administered, the drug's pharmacology and pharmacokinetics, and whether use of the medication will compromise the participant's safety or interpretation of the data. It is the investigator's responsibility to ensure that details regarding the concomitant medications are adequately recorded in the eCRF.

3.4 Study Procedures

Before performing any study procedures, all potential participants will sign an informed consent form (ICF) (as detailed in [Section 5.3](#)). Participants will undergo study procedures at the time points specified in the Schedule of Events ([Table 9](#)).

After participant proceeds to the open-label Part B of the study at the Participant Decision Clinic Visit ([Table 10](#)), Part A schedule of events ([Table 9](#)) will no longer be followed and become obsolete.

Upon the participant's decision to end participation in Moderna's mRNA-1273-P301 COVE study, and consent to enrolling into Part C of this study, they will follow study procedures as specified in the Schedule of Events ([Table 12](#)).

A participant also can be seen for an unscheduled visit at any time during the study. An unscheduled visit may be prompted by reactogenicity issues or new or ongoing AEs. The site also has the discretion to make reminder telephone calls or send text messages to inform the participant about visits, review eDiary requirements, or follow up on ongoing or outstanding issues.

In accordance with “FDA Guidance on Conduct of Clinical Trials of Medical Products during COVID-19 Public Health Emergency” ([DHHS 2020](#)), investigators may convert study site visits to telemedicine visits with the approval of the Sponsor. Such action should be taken to protect the safety and well-being of study participants and study site staff or to comply with state or municipal mandates.

3.4.1 Assessment for SARS-CoV-2 Infection

Study participants will have nasopharyngeal swab samples collected for SARS-CoV-2 testing at time points specified in the Schedule of Events (Part A [Table 9](#) and Part B [Table 10](#), [Table 11](#) and [Table 12](#), and Part C [Table 12](#)).

For Part A, Part B, and Part C of this study, a study illness visit or a consultation will be arranged within 24 hours or as soon as possible to collect a nasopharyngeal swab sample to ascertain the presence of SARS-CoV-2 via PCR if a participant experiences any of the following:

- Signs or symptoms of SARS-CoV-2 infection as defined by the CDC ([CDC 2020c](#))
- Exposure to an individual confirmed to be infected with SARS-CoV-2
- MAAE suggesting a SARS-CoV-2 infection

Additionally, clinical information will be carefully collected to evaluate the severity of the clinical case. All findings will be recorded in the eCRF.

If scheduled, a study site illness visit may include assessments such as medical history, physical examination, blood sampling for clinical laboratory testing, and nasopharyngeal swab sampling for viral PCR (including multiplex PCR for respiratory viruses including SARS-CoV-2) to evaluate the severity of the clinical case. Radiologic imaging studies may be conducted. Blood samples will be collected at all illness visits for potential future immunologic assessment of SARS-CoV-2 infection.

If participants are confirmed to have SARS-CoV-2 infection, the investigator will notify the participant’s primary care physician of the diagnosis. Additionally, a convalescent visit will be scheduled approximately 28 days after diagnosis. At this visit, a blood sample will be collected for potential future immunologic assessment of SARS-CoV-2 infection.

If participants are confirmed to have SARS-CoV-2 infection, and are asymptomatic, the investigator will notify the participant's primary care physician and local health authority, as per local regulations. If the participant had known exposure to COVID-19 (eg, exposure to someone with confirmed COVID-19 disease), it will be captured in the COVID-19 exposure form, and the participant will be discontinued from future study treatment only, and will continue to follow all other study assessments as outlined in the protocol. Additionally, a convalescent visit will be scheduled approximately 28 days after diagnosis. At this visit, a blood sample will be collected for potential immunologic assessment of SARS-CoV-2 infection.

Any confirmed SARS-CoV-2 infection occurring in participants, except asymptomatic infection diagnosed at Day 1, will be captured as an MAAE along with relevant concomitant medications and details about severity, seriousness, and outcome.

3.4.2 Use of Electronic Diaries

At the time of consent, the participants must confirm they will be willing to complete an eDiary using either an application downloaded to their smartphone or using a device that is provided at the time of enrollment. Before enrollment on Day 1, the participant will be instructed to download the eDiary application or will be provided an eDiary device to record solicited ARs (Section 3.4.8.4) beginning on Day 1 or at the Participant Decision Visit in the open-label Part B of the study.

In Part A, at each injection visit, participants will be instructed (Day 1) or reminded (Day 29) on thermometer usage to measure body temperature, ruler usage to measure injection site erythema and swelling/induration (hardness), and self-assessment for localized axillary swelling or tenderness on the same side as the injection arm.

In Part B and Part C, at the respective injection visit, participants will be reminded on thermometer usage to measure body temperature, ruler usage to measure injection site erythema and swelling/induration (hardness), and self-assessment for localized axillary swelling or tenderness on the same side as the injection arm.

At each injection visit, participants will record data into the eDiary starting approximately 30 minutes after injection under supervision of the study site staff to ensure successful entry of assessments. The site staff will perform any retraining as necessary. Study participants will continue to record data in the eDiary after they leave the study site, preferably in the evening and at the same time each day, on the day of injection and for 6 days following injection.

Participants will record the following data in the eDiary:

- Solicited local and systemic reactogenicity ARs, as defined in [Section 3.4.8.4](#), that occur on the day of each vaccine administration and during the 7 days after vaccine administration (ie, the day of injection and 6 subsequent days). Any solicited AR that is ongoing beyond Day 7 will be reported in the eDiary until resolution. Adverse reactions recorded in diaries beyond Day 7 should be reviewed by study site staff either during the next scheduled telephone call or at the next study site visit ([Table 9](#), [Table 11](#), and [Table 12](#)).
- Daily oral body temperature measurement should be performed at approximately the same time each day using the thermometer provided by the study site. If body temperature is taken more than once in a given day, only the highest temperature reading should be recorded.
- Measurement, as applicable, for solicited local ARs (injection site erythema and swelling/induration); the size measurements will be performed using the ruler provided by the study site.
- Participants will be queried by the eDiary whether any medications were taken to treat or prevent pain or fever on a day of injection or for the 6 subsequent days.

The eDiary will be the only source documents allowed for solicited systemic or local ARs (including body temperature measurements). Participants will be instructed to complete eDiary entries daily. The participant will have a limited window on the following day to complete assessments for the previous day; quantitative temperature recordings and measurement of any injection site erythema or swelling/induration reported on the following day may be excluded from the analyses of solicited ARs.

Any new safety information reported during safety telephone calls or at site visits (including a solicited reaction) that is not already captured in the eDiary will be described in the source documents as a verbally reported event. Any AR reported in this manner must be described as an unsolicited event and therefore entered on the AE eCRF.

Study site staff will review eDiary data with participants at the Day 8 and Day 36 visits in the blinded Part A of the study. In the open-label Part B of the study, eDiary data will be reviewed in person on open-label (OL) Day 8 for participants receiving a single booster ([Table 12](#)) and via phone call 7 days after each vaccination for those participants receiving 2 doses of 100 µg mRNA-1273 ([Table 11](#)). In Part C of the study, eDiary data will be reviewed in person on open-label Day 8 ([Table 12](#)).

The eDiary will also be used after the Day 57 visit (including OL-Day 57 in Part B and Part C) to capture the occurrence of AEs, MAAEs, SAEs, or AEs leading to study withdrawal, every 4 weeks from Day 71 through Day 183 in Part A ([Table 9](#)), from OL-Day 71 through OL- Day 155 in Part B ([Table 11](#) and [Table 12](#)) and Part C ([Table 12](#)), and from Day 223 through Day 363 in Part A only ([Table 9](#)).

The eDiary will prompt the participant to complete an eDiary questionnaire that collects the following data:

- Changes in health since last completing the questionnaire or since last in contact with the study site.
- Known exposure to someone with known COVID-19 or SARS-CoV-2 infection.
- Any experience of symptoms of COVID-19.
- Any MAAEs or SAEs.

If an eDiary record results in identification of relevant safety events according to the study period or of symptoms of COVID-19, the site will follow up with the participant via telephone and assess the need for an unscheduled visit.

Completion of eDiary questionnaires will alternate with safety telephone calls ([Section 3.4.3](#)) as the procedure for safety follow-up approximately every 2 weeks after the Day 57 ([Table 9](#)) or the OL-Day 57 visit ([Table 11](#) and [Table 12](#)).

3.4.3 Safety Telephone Calls

A safety telephone call is a telephone call made to the participant by trained site personnel. This call will follow a script, which will facilitate the collection of relevant safety information.

In blinded Part A, safety telephone calls are scheduled to occur every 4 weeks from Day 85 through Day 197 and from Day 237 through Day 377 ([Table 9](#)).

In the open-label Part B, the safety telephone calls are scheduled to occur every 4 weeks ([Table 11](#) and [Table 12](#)).

In the open-label Part C, the safety telephone calls are scheduled to occur every 4 weeks ([Table 12](#)).

The participant will be interviewed according to the script about occurrence of AEs, MAAEs, SAEs, AEs leading to study withdrawal, concomitant medications associated with those events, and any non-study vaccinations ([Section 3.4.8.6](#)). In addition, study personnel will collect information on known participant exposure to someone with known COVID-19 or SARS-CoV-2

infection and on participant experience of COVID-19 symptoms. All safety information collected from the telephone contact must be documented in source documents as described by the participant and not documented on the script used for the safety telephone contact.

3.4.4 Safety Laboratory Assessments

In the blinded Part A of the study, laboratory tests will be performed by the central laboratory unless otherwise specified. Screening safety laboratory tests will include complete blood count with differential, alanine aminotransferase (ALT), aspartate aminotransferase (AST), total and direct bilirubin, alkaline phosphatase (ALP), blood urea nitrogen/creatinine, prothrombin time (PT), and partial thromboplastin time (PTT). These safety laboratory tests are to be repeated at Day 29 and Day 57 only for Cohort 2 (≥ 55 years of age).

Additional tests include the following:

In both Parts A and B, a point-of-care urine pregnancy test will be performed at the Screening Visit (Day 0) or Participant Decision Visit (OL-Day 1) and before each vaccine administration. In Part C, a point-of-care urine pregnancy test will be performed at the OL-Day 1 prior to vaccine administration.

At any time, a pregnancy test either via blood or point-of-care urine can be performed, at the discretion of the investigator.

- If not documented in a female participant's medical records, an FSH test may be performed at the Screening Visit (Day 0, Part A, Blinded Phase only), as necessary and at the discretion of the investigator, to confirm postmenopausal status.
- Hepatitis B surface antigen, hepatitis C virus antibody, and HIV virus (types 1 and 2) antibody at the Screening Visit (Day 0, Part A, Blinded Phase only).

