Part C, the Open-Label Interventional Phase of the study of mRNA-1273.351 and mRNA-1273/mRNA-1273.351 mixture booster vaccines, is prompted by the need to pro-actively prepare for vaccination strategies that induce a broader protection, including variants such as B.1.351. This proof-of-concept study design will evaluate the safety and immunogenicity of two dose levels of mRNA-1273.351 (20 µg and 50 µg), and mRNA-1273/mRNA-1273.351 mixture (50 µg total), given as a single IM injection booster. Upon meeting eligibility criteria, approximately 60 participants from Moderna's Phase 3 mRNA-1273-P301 COVE study will be enrolled into this Part C to receive a single IM injection of mRNA-1273.351 (20 µg or 50 µg) or a single IM injection of mRNA-1273/mRNA-1273.351 mixture (50µg). An additional booster dose may be added approximately 56 days after the first boost at OL-D1. This additional booster dose will be triggered following review of immunogenicity data up to OL-D15 of the initial mRNA-1273.351 (20 µg and 50 µg) and mRNA-1273/mRNA-1273.351 mixture injections.

Study Population:

Participants (males and females 18 years of age or older at time of consent) will be included in the study if they are in good health according to the assessment of the investigator and can comply with study procedures. Negative pregnancy tests will be required at Screening and before vaccine administration for female participants of childbearing potential. The full lists of inclusion and exclusion criteria are provided in the body of the protocol.

Safety Assessments:

Safety assessments will include monitoring and recording of the following for each participant:

- Solicited local and systemic ARs that occur during the 7 days following each injection (ie, the day of injection and 6 subsequent days); solicited ARs will be recorded daily using eDiaries. (Part A, Blinded Phase, Part B, Open Label, and Part C, Open Label).
- Unsolicited AEs observed or reported during the 28 days following each injection (ie, the day of injection and 27 subsequent days); unsolicited AEs are AEs that are not included in the protocol-defined solicited ARs. (Part A, Blinded Phase, Part B, Open Label, and Part C, Open Label).
- AEs leading to discontinuation from dosing and/or study participation from Day 1 through Day 394 (Part A) and OL-Month 6 or 7 (Part B and Part C) or withdrawal from the study.

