- Prescription hormonal contraceptive taken or administered via oral (pill), transdermal (patch), subdermal, or IM route
- Sterilization of a female participant's monogamous male partner prior to entry into the study

Note: periodic abstinence (eg, calendar, ovulation, symptothermal, post-ovulation methods) and withdrawal are not acceptable methods of contraception.

3. Male participants engaging in activity that could result in pregnancy of sexual partners must agree to practice adequate contraception and refrain from sperm donation from the time of the first injection and through 3 months after the last injection.

Adequate contraception for male participants is defined as:

- Monogamous relationship with a female partner using an intrauterine device or hormonal contraception (described above)
- Use of barrier methods and spermicide
- History of surgical sterilization
- Male participants with partners who have become pregnant prior to Screening are eligible to participate in the study.

3.1.6.2 Inclusion criterion specific for Part C:

1. Female participants of nonchildbearing potential may be enrolled in the study. Nonchildbearing potential is defined as surgically sterile (history of bilateral tubal ligation, bilateral oophorectomy, hysterectomy) or postmenopausal (defined as amenorrhea for ≥ 12 consecutive months prior to Screening (Day 0) without an alternative medical cause). The FSH level may be measured at the discretion of the investigator to confirm postmenopausal status.
2. Female participants of childbearing potential may be enrolled in the study if the participant fulfills all the following criteria:
 - Has a negative pregnancy test at Part C OL-Day 1 and on the day of injection.
 - Has practiced adequate contraception or has abstained from all activities that could result in pregnancy for at least 28 days prior to the injection (OL-Day 1).
 - Has agreed to continue adequate contraception through 3 months following the second injection (OL-Day 57), as applicable.
 - Is not currently breastfeeding.
3. Adequate female contraception is defined as consistent and correct use of a Food and Drug Administration (FDA) approved contraceptive method in accordance with the product label. For example:
 - Barrier method (such as condoms, diaphragm, or cervical cap) used in conjunction with spermicide
 - Intrauterine device

- Prescription hormonal contraceptive taken or administered via oral (pill), transdermal (patch), subdermal, or IM route

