3.3.2.2 Contraindications to Subsequent Injection

Prior to receiving a second injection, participants will be reassessed to ensure that they continue to meet eligibility requirements as outlined below. For Part C, if the option to administer a second injection is exercised, prior to receiving a second injection, participants will be reassessed to ensure they continue to meet eligibility requirements as outlined below.

The following events in a participant constitute absolute contraindications to any further administration of the investigational product to that participant. If any of these events occur during the study, the participant must not receive additional doses of vaccine but will be encouraged to continue study participation for safety through 6 months following last injection ([Section 3.2.5](#)).

- Symptomatic COVID-19 at the time of a second injection. If COVID-19 is suspected on or prior to administration of a second injection, further administration of investigational product must be withheld, as applicable, until COVID-19 test results are available.
- Anaphylaxis or systemic hypersensitivity reaction following the administration of vaccine.
- Any SAE judged by investigator or Sponsor to be related to study vaccine.
- Pregnancy
- Any clinically significant medical condition that, in the opinion of the investigator, poses an additional risk to the participant if he/she continues to participate in the study.

The following events constitute contraindications to administration of study vaccine at certain points in time, and if any of these events occur at the time scheduled for injection, the participant may be injected at a later date, within the time window specified in the Schedule of Events (Section 7.1), or the participant may be withdrawn from dosing at the discretion of the investigator (Section 3.2.5):

- Acute moderate or severe infection with or without fever at the time of injection
- Fever, defined as body temperature $\geq 38.0^{\circ}\text{C}$ (100.4°F) at the time of injection

Participants with a minor illness without fever, as assessed by the investigator, can be administered investigational product. Participants with a fever of 38.0°C (100.4°F) or higher will be contacted within the time window acceptable for participation and reevaluated for eligibility.

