8. All concomitant medications and non-study vaccinations will be recorded through 28 days injection; all concomitant medications relevant to or for the treatment of an SAE or MAAE will be recorded from Day 1 through the final visit (OL-Day 209).
9. Blood sample for serology will be collected only at the Participant Decision Visit.

Approved

Table 12: Part B and Part C: Open-label Schedule of Events (Participants Receiving a Booster Dose)⁹

Visit Number	0	OL-1	OL-2	OL-3	OL-4	OL-5				OL-6
Type of Visit	C	C	C	C	C	C	SC	SFU		C
Month Timepoint	OL-M0				OL-M1	OL-M2		eDiary	SC	OL-M6
Study Visit Day	OL-D1/ Participant Decision Visit ^{1,2}	OL-D8	OL-D15	OL-D29	OL-D57	OL-D64 ¹²	Every 4 weeks OL-D71– OL-D155 ³	Every 4 weeks OL-D85– OL-D169		OL-D181
Window Allowance (Days)		+3	±3	+7	-3/+7	+3	±2	±3	±14	
Days Since Most Recent Injection	0	7	14	28	56	7	--	--	180	
Informed consent form	X									
Confirm participant meets inclusion and exclusion criteria	X									
Physical examination including vital signs ⁴	X			X	X					X
Pregnancy testing	X									
Study injection (including 30-minute post-dosing observation period)	X					X ¹¹				
Blood for serology ¹⁰ and immunogenicity ⁵	X	X	X	X	X					X
Nasopharyngeal swab sample for SARS-CoV-2 ⁶	X			X	X					
eDiary activation for recording solicited adverse reactions (7 days) ⁷	X				X ¹²					
Review of eDiary		X				X ¹²				
Follow-up safety calls ⁸								X		
Recording of unsolicited AEs	X	X	X	X	X ¹²	X ¹²				

Visit Number	0	OL-1	OL-2	OL-3	OL-4	OL-5				OL-6
Type of Visit	C	C	C	C	C	C	SC	SFU		C
Month Timepoint		OL-M0			OL-M1	OL-M2		eDiary	SC	OL-M6
Study Visit Day	OL-D1/ Participant Decision Visit ^{1,2}	OL-D8	OL-D15	OL-D29	OL-D57	OL-D64 ¹²	Every 4 weeks OL-D71– OL-D155 ³	Every 4 weeks OL-D85– OL-D169		OL-D181
Window Allowance (Days)		+3	±3	+7	-3/+7	+3	±2	±3	±14	
Days Since Most Recent Injection	0	7	14	28	56	7	--	--	180	
Recording of MAAEs and concomitant medications relevant to or for the treatment of the MAAE ⁹	X	X	X	X	X	X	X	X	X	X
Recording of SAEs and concomitant medications relevant to or for the treatment of the SAE ⁹	X	X	X	X	X	X	X	X	X	X
Recording of concomitant medications and non-study vaccinations ⁹	X	X	X	X	X ¹²	X ¹²				
Study Completion										X

Abbreviations: AE = adverse event; C = clinic visit; ICF = informed consent form; M = month; MAAE = medically attended AE; SC = safety (telephone) call; SFU = Safety Follow Up; SAE = serious adverse event.

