7. Diary entries will be recorded by the participant starting approximately 30 minutes after injection while at the study site with instruction provided by study staff. Study participants will continue to record in the eDiary each day after they leave the study site, preferably in the evening and at the same time each day, on the day of injection and for 6 days following injection. Any solicited AR that is ongoing beyond Day 7 will be reported in the eDiary until resolution. Adverse reactions recorded in eDiaries beyond Day 7 should be reviewed either during the next telephone call or at the next study site visit.
8. Trained site personnel will call all participants to collect information relating to any AEs, MAAEs, SAEs, AEs leading to study withdrawal, information on concomitant medications associated with those events, and any non-study vaccinations. In addition, study personnel will collect information on known participant exposure to someone with known COVID-19 or SARS-CoV-2 infection and on participant experience of COVID-19 symptoms. Sites will collect this information for diary days only if diary responses indicate the need for follow-up via telephone.
9. All concomitant medications and non-study vaccinations will be recorded through 28 days injection; all concomitant medications relevant to or for the treatment of an SAE or MAAE will be recorded from OL-Day 1 through the final visit (OL-Day 181).

NOTE: The following participants will complete the described assessments in this SOE at OL-Day 1, and will skip OL-D8, OL-D15, OL-Day 29, and OL-D57:

- Participants who received 1 or 2 doses of mRNA-1273 in Part A and decline receiving booster mRNA-1273 in Part B.
- Participants who decline unblinding
- Participants who received placebo in Part A, but decline to receive 2 doses of mRNA-1273 in Part B

Participants who decline receiving booster mRNA-1273, decline unblinding, or decline to receive 2 doses of mRNA-1273 in Part B will not receive study vaccination at OL-D1 (or OL-D29), will not perform a pregnancy test, or eDiary activation at OL-D1.

10. Blood sample for serology will be collected only at the Participant Decision Visit (OL-D1).
11. In Part C, an additional booster dose may be added approximately 56 days after the first boost at OL-D1. This additional booster dose will be triggered following review of immunogenicity data up to OL-D15 of the initial mRNA1273.351 (20 μg and 50 μg) and mRNA-1273/mRNA-1273.351 mixture injections.

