12. If the additional booster dose is given at OL-D57, an eDiary for reactogenicity will be completed for 7 days post-injection. Additionally, unsolicited AEs will continue to be collected for 28 days post last injection.

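### No pregnancy test is scheduled before the optional Part C second injection at OL-D57, although pregnancy is an absolute contraindication to it

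*Protocol*

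**What the plan says.** **The second injection.** Footnote 11 to Protocol Table 12 (Section 7.1) provides: "In Part C, an additional booster dose may be added approximately 56 days after the first boost at OL-D1". Footnote 12 ties the dose to a visit and adds data collection: "If the additional booster dose is given at OL-D57, an eDiary for reactogenicity will be completed for 7 days post-injection". It also extends unsolicited AE collection to 28 days after the last injection. Neither footnote mentions a pregnancy test.

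**The contraindication.** Section 3.3.2.2 lists pregnancy among the absolute contraindications to further dosing: "If any of these events occur during the study, the participant must not receive additional doses of vaccine". The section applies its reassessment expressly to a Part C second injection, should that option be used. It does not say how pregnancy is to be detected.

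**The tests.**
- Section 3.4.4, Parts A and B: a urine test at Screening or the "Participant Decision Visit (OL-Day 1) and before each vaccine administration".
- Section 3.4.4, Part C: "In Part C, a point-of-care urine pregnancy test will be performed at the OL-Day 1 prior to vaccine administration".
- Table 12: the row headed "Pregnancy testing" has one mark, at OL-D1.
- Part C SAP Section 6.3.3: Screening and, before vaccination, OL-Day 1, with further tests as needed at unscheduled visits.
- Synopsis, Study Population: "Negative pregnancy tests will be required at Screening and before vaccine administration for female participants of childbearing potential". This is not restricted by part or by dose.

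**The concern.** A contraindication protects a participant only if something in the schedule would reveal it. For the Part C second injection, the texts that direct site activity stop at OL-Day 1, while the Synopsis and Section 3.3.2.2 reach further. A site working from Table 12 and Section 3.4.4 could do everything marked there and still give a second dose to a participant whose pregnancy had not been detected, which Section 3.3.2.2 forbids.

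The pattern looks like an incomplete update. Several consequences of an OL-D57 dose were carried through: the diary, AE collection, and a contraception commitment running to 3 months after the second injection. The pregnancy-testing row was not changed. Table 12 footnote 4 likewise still gives OL-Day 1 as the only injection day for vital signs. No passage gives a reason for omitting the test.

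**Working it through.** **Step 1: reproduce the plan's own day counts.** Days since OL-D1 = study day − 1.

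| Visit | Calculation | Table 12, days since most recent injection |
|---|---|---|
| OL-D8 | 8 − 1 = 7 | 7 |
| OL-D15 | 15 − 1 = 14 | 14 |
| OL-D29 | 29 − 1 = 28 | 28 |
| OL-D57 | 57 − 1 = 56 | 56 |

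All four agree with Table 12, and 56 agrees with the interval in footnote 11.

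**Step 2: age of the last scheduled test at the second injection.** The only scheduled Part C test is at OL-D1. Table 12 gives OL-D57 a window of −3/+7 days.

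- Earliest dosing day: 57 − 3 = 54; test age 54 − 1 = 53 days.
- Nominal: 57 − 1 = 56 days.
- Latest dosing day: 57 + 7 = 64; test age 64 − 1 = 63 days.

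**Step 3: compare the two-injection schedules.**

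| Schedule | Second injection | Test scheduled at that visit? | Age of previous scheduled test at that visit (ordinary window) |
|---|---|---|---|
| Part A, Table 9 | Day 29, +7 | Yes | 28 to 35 days |
| Part B two-dose, Table 11 | OL-D29, +7 | Yes | 28 to 35 days |
| Part C optional second dose, Table 12 | OL-D57, −3/+7 | No | 53 to 63 days |

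For Parts A and B: 29 − 1 = 28 and 29 + 7 − 1 = 35. The protocol schedules a new test after the shorter gap and none after the longer one.

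**Step 4: set the passages side by side for the second Part C injection.**

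| Text | What it gives |
|---|---|
| Section 3.3.2.2 | Pregnancy bars the dose; reassessment required; no test named |
| Synopsis, Study Population | Negative test before vaccination, no dose or visit specified |
| Section 3.4.4 | Part C test placed at OL-Day 1; other tests discretionary |
| Table 12, footnotes 11 and 12 | Injection, diary and AE collection added; no test |
| Part C SAP 6.3.3 | OL-Day 1; other tests as needed at unscheduled visits |

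**Reading of the table.** In the text as extracted, the mark for the second injection is displaced towards OL-D64. Footnote 12 and the 56-day interval both place the dose at OL-D57, so that visit is used here.

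**The case against.** Several points on the other side stand.

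- **Testing at OL-D57 is allowed.** Section 3.4.4 permits a test at any time at the investigator's discretion, the Part C SAP foresees tests at unscheduled visits, and Section 3.3.2.2 requires reassessment. A reader might infer that the criteria and the schedule cannot both be followed. The documents do not support that: a site that tests at OL-D57 breaches nothing, and Section 3.4.4 does not say that OL-Day 1 is the only permitted occasion. But discretion is not a scheduled check, and Parts A and B have scheduled tests alongside the same discretion.
- **The Synopsis may already supply the requirement.** Read plainly, it covers any injection. What remains is that Section 3.4.4, Table 12 and the Part C SAP do not carry it through to OL-D57.
- **Contraception is addressed.** Section 3.1.6.2 requires contraception or abstinence for at least 28 days before OL-Day 1, and agreement to continue contraception to 3 months after the OL-D57 injection where applicable. This lowers the risk. It does not establish pregnancy status, and Parts A and B combine a similar commitment with a repeat test.

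Two further stronger readings also fail. Inclusion criterion 2 for Part C ("Has a negative pregnancy test at Part C OL-Day 1 and on the day of injection") might seem to require a test on the second injection day. It is an enrolment criterion, and the item after it ties the injection to OL-Day 1, so it is not relied on here. Nor are all of the roughly 60 participants affected: men and women of nonchildbearing potential are outside the testing rule.

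**Conclusion.** The point holds as an inconsistency in **scheduled** testing. Three operational texts place the Part C test at or before OL-Day 1, while the contraindication and the Synopsis extend to a second injection. Followed literally, Table 12 leaves 53 to 63 days between the last scheduled test and that injection.

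This rests on three assumptions: the second injection is given at the OL-D57 visit within its stated window, the first injection and test are on OL-D1, and no discretionary or Synopsis-driven test is done in between. The group at issue is participants of childbearing potential within about 60. The documents do not give their number, so no count is offered. The dose is conditional on immunogenicity review and may never be given. These limits narrow the reach of the problem, but an absolute contraindication should not depend on which section a site happens to consult.

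**What to change.** Before the second-injection option is exercised, the sponsor should reconcile the Synopsis (Study Population), Section 3.3.2.2, Section 3.4.4, Table 12 with footnotes 11 and 12, and Part C SAP Section 6.3.3, so that all state in the same way how pregnancy status is established before a Part C second injection. The clinical rule is for the sponsor to set. The SAP change is secondary, since that section plans only a listing, but it should match whatever the protocol says.

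The cost is protocol and SAP wording, with the usual amendment approval. If the reconciled text calls for a test, OL-D57 is already a clinic visit and the point-of-care urine test is already in use in the trial.
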